- 16) Known hypersensitivity or allergy to the active ingredient or excipients of SL-901.
- 17) Breast-feeding females.

[figure not shown]
Test Products, Doses, and Mode of Administration:	In Part 1a, the SL-901 starting dose on the 20 mg on both the QD and BID schedule. Dose levels planned to be tested in both QD and BID schedules will be tested in parallel, with enrollment to the current cohort for each schedule conducted on an every other patient basis (see Table 5). A treatment cycle is 28 days, with daily dosing throughout the cycle. The regimen of SL-901 for Part 1b of the study will be based on the clinical experience from Part 1a.
Duration of Treatment:	Patients whose disease has not progressed and who have not discontinued due to toxicity, may continue to receive additional cycles of SL-901 at the same dose and schedule.

[figure not shown]

[figure not shown]
Safety:	
Patients' medical history will be collected during Screening and updated prior to the first SL-901 dose. Safety assessments include physical examinations, safety laboratories (clinical chemistry, hematology, and coagulation), vital signs and weight, ECOG performance status, and electrocardiograms (ECGs) (performed according to the schedule in Table 8). Assessment of AEs and concomitant medications will be performed for each patient throughout the study.
 
An End-of-Treatment (EOT) visit to include safety laboratory evaluation plus adverse events and concomitant medication checks, will be conducted 30 days after the last dose of SL-901.

Efficacy:	
Tumor assessment by will occur at Screening (for identification of baseline disease) and after every 2 cycles of treatment thereafter. Response will be evaluated using Response Evaluation Criteria in Solid Tumors (RECIST) v1.1 (Eisenhauer 2009).
 
After completion of the EOT visit, patients will then be followed every 90 days for survival status for 12 months. The survival follow-up may be by telephone contact. If the patient discontinued study drug for reasons other than progressive disease, disease assessments should continue to be performed on an every 8-week basis (± 1 week) through 6 months after the first study drug dose and then on an every 90-day basis or until, in the judgment of the Investigator, there is evidence of relapsed or progressive disease.

Statistical Methods:	Study data will be reviewed in accordance with the Statistical Analysis Plan described in Section 9.3 .

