7.3. Treatment Discontinuation

Study drug may be discontinued for any of the following reasons:

- Progression of disease that, in the opinion of the Investigator, precludes further study treatment. After consultation with the Sponsor, SL-901 may be continued for a patient who has met the criteria for progressive disease but in the Investigator's opinion, continues to derive benefit from study treatment.
- Occurrence of an unacceptable AE, including DLT.
- Pregnancy.
- SL-901 interruption due to study drug-related toxicity for >1 cycle (i.e., >28 days). Interruptions or delays >28 days for reasons other than AEs and/or in the setting of sustained disease control may be acceptable and are to be discussed with the Medical Monitor.
- Patient requires use of a prohibited concomitant medication or therapy.
- General or specific changes in the patient's condition unacceptable for further treatment within the study parameters, in the judgment of the Investigator.
- Non-compliance.

- Lost to follow-up.
- Patient withdrawal of consent.
- Sponsor request.
- Other.

All study procedures outlined for the End-of-Treatment (EOT) visit should be performed 30 days (± 3 days) after the last study drug dose.

In Part 1a, patients who receive <75% of the planned SL-901 doses in C1 and/or discontinue from the study before completing study assessments through C2D1 for reasons other than DLT are to be replaced.

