min [max(PD date + 1, last SL-901 dose date + 1), end date of new anti-cancer therapy].

Last study drug administration

The following rules should be used for the imputation of date of last SL-901 administration:

- If the date of last administration is completely missing and there is no EOT eCRF and no death date, the subject is considered as ongoing and the cut-off date should be used as the last dosing date.
- If the date of last administration is completely or partially missing and the EOT eCRF is available (prior to any death date or withdrawal of consent date, if available):
 - Case 1: The date of last administration is completely missing, and the EOT visit date is complete, then this latter date should be used.
 - Case 2: Only Year(yyyy) of the dose end date is available and yyyy < the year of EOT date:
Use Dec31yyyy
 - Case 3: Only Year(yyyy) of the dose end date is available and yyyy = the year of EOT date:
Use EOT date
 - Case 4: Both Year(yyyy) and Month (mm) are available for the date of last administration, and yyyy = the year of EOT date and mm < the month of EOT visit: Use the last day of the Month (mm).
 - Use min (EOT date, death date) for all other cases.

After imputation, compare the imputed date with the start date of that specific record, if the imputed date is < start date of that record: Use the start date of that record.

Tumor Assessment

Completely or partially missing Tumor Assessment (TA) dates will not be imputed.

- In case date of last TA is missing and there are no previous TA dates, then the date of first study drug admin will be used for censoring

- In case date of last TA is missing and there are previous TA dates, then the previous TA date will be used for censoring
- If there are multiple scan dates associated with an evaluation, the earliest of the scan dates associated with the evaluation will be used as the date of assessment.

Handling of PK concentrations Below the Lower Limit of Quantification and missing sampling timepoints

In all data presentations (except listings), plasma concentration values below the lower limit of quantification (BLQ) will be set to zero before the t_{max} and to “missing” after the t_{max} . Data-replacements will be implemented by the PK analyst from Clinical Pharmacology and Pharmacometrics department.

In listings, BLQ values will be reported as “BLQ”.

A footnote will be added to the listing, tables, and figures, to indicate the lower limit of quantification (LOQ) value.

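### SAP 11.3, last-dose imputation: a known month in the year before the EOT visit misses Case 4 and is dated at the EOT visit, outside the recorded month

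*SAP*

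**What the plan says.** The rules are in SAP 11.3 under the last study drug administration. They apply when the date is wholly or partly missing and "the EOT eCRF is available (prior to any death date or withdrawal of consent date, if available"). Within that branch:

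- **Case 1**, nothing known: use the EOT date.
- **Case 2**, "Only Year(yyyy) of the dose end date is available and yyyy < the year of EOT date": use 31 December of the recorded year.
- **Case 3**, "Only Year(yyyy) of the dose end date is available and yyyy = the year of EOT date": use the EOT date.
- **Case 4**, month and year both known, and "yyyy = the year of EOT date and mm < the month of EOT visit: Use the last day of the Month (mm").
- **Catch-all**: "Use min (EOT date, death date) for all other cases".

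One check follows imputation: "if the imputed date is < start date of that record: Use the start date of that record".

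On visit timing, Protocol 7.3 states "All study procedures outlined for the End-of-Treatment (EOT) visit should be performed 30 days" after the last dose, with a window of 3 days either side. The Protocol synopsis says the visit "will be conducted 30 days after the last dose of SL-901".

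**The concern.** Year-only dates have a rule for an earlier year (Case 2) and for the EOT year (Case 3). Dates with a known month have a rule only for the EOT year (Case 4). A known month in the earlier year therefore goes to the catch-all.

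The result contradicts the record, and it also reverses the value of information: knowing the month gives a worse date than knowing only the year. The visit schedule makes this the normal outcome for a December last dose with a missing day, because EOT then usually falls in January.

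SAP 11.5.10 uses the last-dose date for treatment duration, which is the denominator of actual and hence relative dose intensity. The date also sets the end of the TEAE window (SAP 7.2.2). In SAP 11.3 it limits the imputed start of new anti-cancer therapy.

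**Working it through.** **Inputs.** Case logic from SAP 11.3; EOT lag of 27 to 33 days from Protocol 7.3; exposure formulas from SAP 11.5.10. Calendar years below are illustrative.

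**1. Trace one record.** True last dose 10 Dec 2021, recorded as December 2021, EOT 9 Jan 2022 (lag 30).
- Cases 1 to 3 do not apply, because the month is known.
- Case 4 fails, because 2021 is not the EOT year.
- The catch-all gives the earlier of EOT and death. The branch requires EOT to precede any death, so the result is 9 Jan 2022.
- The check after imputation can only move a date later, so it does not help.

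Two comparisons show the inconsistency. The same patient with only 2021 recorded gets 31 Dec 2021 from Case 2. A last dose on 10 Nov 2021 with EOT on 10 Dec 2021 is held at 30 Nov 2021 by Case 4.

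**2. How often the condition is met.** Take every last-dose day in a 365-day year with each lag from 27 to 33 days, equally weighted. At lag L, exactly L last-dose days have an EOT in the next year.
- Whole year: (27 + 28 + 29 + 30 + 31 + 32 + 33) / (365 × 7) = 210 / 2,555 = 8.2%.
- December only: (27 + 28 + 29 + 30 + 31 + 31 + 31) / (31 × 7) = 207 / 217 = 95%.
- The other 3 of the 210 are last doses on 29 or 30 November with a lag of 32 or 33 days.
- Of the 207, 204 are dated in January and 3 on 1 or 2 February (30 December at lag 33; 31 December at lags 32 and 33).

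**3. Size of the date error.**

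| Rule | Error against true date | Distance beyond recorded month |
|---|---|---|
| As written | 27 to 33 days, mean 6,328 / 210 = 30.1 | 1 to 33 days, mean 3,362 / 210 = 16.0 |
| Case 4 comparing year and month | 0 to 30 days, mean 2,966 / 210 = 14.1 | none |

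**4. Effect on exposure.** Cumulative dose comes from capsule counts and does not change. With true duration T and date error e, dose intensity is multiplied by T / (T + e). For the record in step 1, e = 30 as written and e = 21 with the repaired rule. T is assumed: a 5-day run-in plus one, two or four 28-day cycles.

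| T (days) | As written | Repaired |
|---|---|---|
| 33 | 33/63 = 0.52 | 33/54 = 0.61 |
| 61 | 61/91 = 0.67 | 61/82 = 0.74 |
| 117 | 117/147 = 0.80 | 117/138 = 0.85 |

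One such date raises a cohort's mean duration by 30/3 = 10 days with 3 patients, or 30/6 = 5 days with 6. Under the repaired rule the rise is 7 or 3.5 days.

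**5. Expected number of records.** The documents give no count of last-dose dates lacking a day. At the Part 1a ceiling of 60 patients, and assuming 2%, 5% or 10% lack only the day: 60 × 0.02 × 0.082 = 0.1, 60 × 0.05 × 0.082 = 0.25, 60 × 0.10 × 0.082 = 0.5 patients.

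**The case against.** The catch-all is explicit, so the outcome is defined and leaves the programmer no discretion. That is right: the defect is a poor default value. It is still hard to read as a deliberate choice, since the AE stop-date rule in the same section takes the last day of a known month with no year condition.

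The gain is also partial. Even the repaired rule leaves a mean error of 14.1 days, and Cases 1 and 3 use EOT as a proxy by design. Those cases, however, do not contradict a recorded month.

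Missing days should be uncommon, given patient diaries (SAP 11.5.10), dispensing and return records (Protocol 6.3) and data queries (Protocol 10.1.7). This stands, and it limits the importance of the point.

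A reader might infer three larger consequences that the documents do not support:

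- **TEAEs counted up to about 60 days after the true last dose.** With a true last dose on 16 Dec 2021 and EOT on 15 Jan 2022, the nominal window would run to 14 Feb 2022. But AEs are collected only through 30 days after the last dose (Protocol 8.2.2, SAP 5.2), here 15 Jan 2022. Later events may be listed if recorded (SAP 11.5.2), but their collection is not planned.
- **Shifted censoring for new therapy.** The last-dose date enters only when the therapy start is itself partial or missing. A fully dated start is not moved.
- **A gap that recurs every year.** The SAP, dated 23 May 2023, reports that the study stopped early and that Part 1b was not started. The number of relevant year-ends is limited.

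**Conclusion.** The gap is real and nothing else in the documents closes it. A last dose with known month and year, in the calendar year before the EOT visit, is dated at the EOT visit and outside the recorded month. For an on-schedule EOT the date is 27 to 33 days late. The direction is always the same: longer duration and lower dose intensity.

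The importance is low. The definitions of DLT, MTD, ORR and OS do not use the last-dose date. The 8.2% and 95% figures assume EOT visits on schedule and, for the first, last doses spread evenly over the year; they are shares of dates lacking only the day, not of patients. Under the missingness rates assumed above, fewer than one affected patient is expected. If there is one, the exposure summary of a cohort of 3 to 6 can visibly shift.

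**What to change.** Reword the Case 4 condition in SAP 11.3: year and month are available, and the recorded year-month is earlier than the EOT year-month; use the last day of the recorded month, capped at the death date. Add one sentence: an imputed last-dose date may not fall outside the recorded year and month.

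A last dose in the same month as EOT still takes the EOT date, which already lies inside the recorded month. No other case changes.

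The cost is one condition in the SAP and one in the exposure program. The SAP is to be finalised before database lock, so this belongs in a revision before then. If that is no longer possible, Protocol 9.4 provides for recording the change in the clinical study report. A count of last-dose dates lacking a day would show at once whether any patient is affected.

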11.4. Patient disposition and Baseline tables

Patient Disposition

Patient disposition will be tabulated by cohort and overall, separately for each study part, including the following:

- Number of patients screened
- Number (%) of screening failures, with reason for screening failure
- Number (%) of patients treated (i.e. who received at least one SL-901 dose)
- Number (%) of patients who are still on-treatment (based on the absence of the ‘Disposition Status - Treatment Discontinuation’ eCRF)
- Number (%) of patients who discontinued study treatment (based on the presence of the ‘Disposition Status - Treatment Discontinuation’ eCRF)
- Reason for study treatment discontinuation (based on ‘Disposition Status - Treatment Discontinuation eCRF’)
- Number (%) of patients in each analysis population
- Number (%) of patients who terminated the study with reason for termination (based on the ‘Disposition Status - End of Study’ eCRF)

Demographic and Baseline Characteristics

Demographic and baseline characteristics will be summarized by cohort and overall, separately for each study part, on the Efficacy Population using descriptive statistics; the following variables will be displayed:

- Age, sex, race, ethnicity
- ECOG PS
- Location of primary tumor, disease stage at screening, years from diagnosis (calculated as year of screening visit – year of diagnosis), disease stage at diagnosis, number and setting of previous lines of cancer treatment, best response to previous cancer treatment.
- Tumor mutation status (Part 1a and Part 1b)

By-patient listings will be produced for demography, tumor history, ECOG PS and tumor mutation status.

Medical History, Procedures and Prior Radiotherapy

Medical history will be presented by cohort and overall, separately for each study part, using frequency counts and percentages on the Efficacy Population.

Medical/Procedure History are those conditions which started and ended before the date and time of first SL-901 intake; concomitant medical conditions/procedures are the ones with an end date on or after the date and time of first SL-901 intake, or still ongoing).

The following summaries will be produced by MedDRA system organ class (SOC) and preferred term (PT):

- Medical History
- Procedure History
- Concomitant Medical Conditions
- Concomitant Procedures

Summary of prior radiotherapy will include time from last therapy to first dose of study drug, site of radiotherapy, response to treatment.

Medical/Procedure history, concomitant medical conditions/procedures and prior radiotherapy will also be reported in by-patient listings.

Prior and Concomitant Medications

Prior and Concomitant Medications will be presented by cohort and overall, separately for each study part, using frequency counts and percentages on the Efficacy Population.

Prior medications are those with start and end dates prior to the date and time of first SL-901 intake; concomitant medications are those with start date on or after the date and time of first SL-901 administration; prior and concomitant medications are those with start date prior to the date and time of first SL-901 intake and end date on or after the date and time of first SL-901 intake or still ongoing.

The following summaries will be produced by WHO Drug Global Dictionary PT and Anatomical Therapeutic Chemical (ATC) code level 4:

- Prior Medications
- Prior and Concomitant Medications
- Concomitant Medications

Prior, concomitant and prior and concomitant medications will be reported in by-patient listings.

11.5. Safety analysis

Safety and toxicity will be evaluated on the Safety population by means of descriptive statistics during each study part. Safety evaluations will be based on the incidence, relationship, severity grade, and seriousness of treatment emergent adverse events (TEAEs), ECOG performance status, vital signs, ECGs, physical examination, and laboratory tests of chemistry, hematology, and coagulation parameters, as well as dose modifications (interruptions/reductions) due to TEAEs, and treatment discontinuations due to TEAEs. In addition, study drug exposure and compliance will be summarized.

11.5.1. Safety assessments

Safety and tolerability endpoints will be derived from the following measurements/evaluations:

- Incidence, grade, seriousness, and causality of TEAEs;
- Physical examination;
- Vital signs;
- Safety laboratory tests (Haematology, Serum Chemistry and Coagulation);
- 12-lead-ECG.
- ECOG PS

and will be presented by cohort and overall, separately for each study part, on the Safety population, with the exception of DLTs which will be presented on the DLT population.

11.5.2. Adverse Events

All identified AEs are recorded and described on the appropriate AE page of the eCRF, except for those events occurring prior to the start of the screening period, which are recorded on the Medical History eCRF page. All Adverse Events (including non-TEAEs or AEs happening after End of Study Visit of the patient) recorded in the eCRF will be listed.

The following definitions apply:

- An AE is considered as treatment-related if has been reported as Definitely Related, Probably Related, Possibly Related or if the relationship is missing.
- An AE is leading to drug interruption if action taken with study drug is “Drug interrupted”
- An AE is leading to drug withdrawal if action taken with study drug is “Drug withdrawn”
- An AE is leading to dose reduction if action taken with study drug is “Dose reduced”
- An AE is leading to death if the outcome of the event is “Fatal”

In all summaries, patients with more than one AE under the same SOC or PT are counted only once for that SOC or PT.

For summaries by maximum CTCAE grade, patients with multiple events under the same SOC or PT will be counted only under the category of their most severe event within that SOC or PT.

For summaries by relationship to study drug, events judged to be Definitely Related, Probably Related, Possibly Related will be considered as Treatment-related.

Excluding the general summaries of TEAEs, all other tables will report both the number of patients experiencing events and the number of events.

An overall summary of TEAEs will include the number of patients in the following categories:

- Any TEAE
- Any serious TEAE
- Any related TEAE
- Any serious related TEAE
- Any TEAE by Relationship with study drug
- Any TEAE by Outcome,
- Any TEAE by CTCAE Grade
- Any TEAE by Action Taken
- Any TEAE by Pattern

TEAEs will also be summarized by SOC and PT for the following categories:

- DLTs
- All TEAEs
- TEAEs by Maximum Grade
- TEAEs leading to drug interruption
- TEAEs leading to drug withdrawal
- TEAEs leading to dose reduction
- TEAEs leading to death
- Serious TEAEs (SAEs)
- SAEs by Maximum Grade
- Treatment-related TEAEs
- Treatment-related TEAEs by Maximum Grade
- Treatment-related TEAEs leading to drug interruption
- Treatment-related TEAEs leading to drug withdrawal
- Treatment-related TEAEs leading to dose reduction
- Treatment-related TEAEs leading to death
- Serious Treatment-related TEAEs
- Serious Treatment-related TEAEs by Maximum Grade
-

All adverse events will be listed. At minimum the following information will be reported for all AEs listings: date of onset and resolution, study cycle of occurrence, duration in days, grade and seriousness of the event, relationship to study drug, action taken with study drug.

Listings will be produced for all AEs, all TEAEs, DLTs, SAEs, Treatment-related TEAEs, Serious Treatment-related TEAEs.

11.5.3. Vital Signs

Vital signs will only be listed:

- Height (cm)
- Weight (kg)
- Body Mass Index (BMI, kg/m²), calculated as Weight (kg) / Height (m)²
- Heart Rate (bpm)
- Systolic Blood Pressure (mmHg)
- Diastolic Blood Pressure (mmHg)
- Respiratory Rate (breaths/min)

- Temperature (°C)

11.5.4. Physical Examination

A listing of Physical Examination results will be provided.

11.5.5. 12-lead ECG

ECG parameters will be summarized using descriptive statistics both in terms of absolute values and change from baseline at each visit and time point.

The following parameters will be presented in the summary tables:

- Heart Rate (bpm)
- PR Interval (msec)
- QRS Duration (msec)
- QT Interval (msec)
- QTcF Interval (msec)

In addition, the following categorical analysis on QTcF interval prolongation will be presented according to the ICH E14 guideline:

- Number (%) of subjects with QTcF > 450 msec and ≤480 msec
- Number (%) of subjects with QTcF > 480 msec and ≤500 msec
- Number (%) of subjects with QTcF > 500 msec
- Number (%) of subjects with QTcF change from baseline > 30 msec and ≤60 msec
- Number (%) of subjects with QTcF change from baseline > 60 msec

Overall ECG Interpretation (Normal, Abnormal NCS, Abnormal CS) will only be listed.

All ECG parameters will be listed.

Results from unscheduled visits will not be included in the summary tables but will only be listed.

11.5.6. Echocardiogram

Echocardiogram results (ejection fraction (%) and interpretation) obtained at Screening will be presented by cohort and overall, separately for each study part, using summary statistics on the Safety Population.

11.5.7. Safety laboratory tests

Laboratory parameters, including haematology, chemistry and coagulation, will be summarized using descriptive statistics both in terms of absolute values and change from baseline at each visit.

Laboratory values will be reported in SI units and will be compared to the relevant reference range in SI units and categorized as follows:

- Low: < lower limit of the reference range
- Normal: \geq lower limit of the reference range and \leq upper limit of the reference range
- High: > upper limit of the reference range.

Shift tables of laboratory parameters from baseline to the worst post-baseline low/normal/high categorization will be performed; in the shift tables, percentages will be calculated based on the number of subjects that have valid data for both baseline and at least 1 post-baseline assessment.

For analysis purposes, values preceded by a “<” or “>” sign will be considered equal to the lower or upper limit of quantification, respectively.

All laboratory parameters, including low/normal/high categorization, will be listed.

Results from unscheduled visits will not be included in the summary tables but will only be listed.

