8.5.2. Permitted Concurrent Medications

Medications and treatments other than those specified in [Section 8.5.1](#), including palliative and supportive care for disease-related symptoms (e.g., appetite stimulants, stimulants [modafinil], anti-cachexia therapy [fish-oil supplements], anti-depressants, opiate and non-opiate analgesics, antibiotics, selective use of corticosteroids, and, as indicated below, anti-emetic and anti-diarrheal agents and hematopoietic growth factors), are permitted during the study. In case of hyperglycemia grade 3 or higher, treatment with Metformin is permitted.

Patients should be closely monitored, and treatment is to be instituted for disease-related symptoms, as appropriate.

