9.3.4.1. Laboratory Parameters

Laboratory results (hematology, chemistry and coagulation parameters) will be graded according to NCI CTCAE, Version 5.0 (or higher). Laboratory results not corresponding to an NCI CTCAE term will not be graded. Incidences of laboratory abnormalities will be summarized with descriptive statistics.

Shift tables will be generated to display changes from baseline to the worst value on study and last value on study using values provided by the local laboratory.

All laboratory data will be included in listings and abnormal results will be flagged.

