[Table 14.3.5.3: Hematology by Visit](#)

[Table 14.3.5.4: Blood Chemistry by Visit](#)

[Table 14.3.5.5: Coagulation by Visit](#)

[Table 14.3.5.6: Hematology – Shift to Worst Post-Baseline Category](#)

[Table 14.3.5.7: Blood Chemistry – Shift to Worst Post-Baseline Category](#)

[Table 14.3.5.8: Coagulation – Shift to Worst Post-Baseline Category](#)

[Table 14.3.5.9: ECOG Performance Status](#)

[Table 14.3.5.10: ECOG Performance Status – Shift to Worst Post-Baseline Value](#)

Table 14.3.5.11: Echocardiogram**Table 14.2.1: Best Overall Response and Objective Response – Investigator's Assessment (RECIST v1.1)****Table 14.2.2: Duration of Response - Investigator's Assessment (RECIST v1.1)****Table 14.2.4: Duration of Complete Response - Investigator's Assessment (RECIST v1.1)****Table 14.2.6: Progression-free Survival - Investigator's Assessment (RECIST v1.1)****Table 14.2.8: Overall Survival - Investigator's Assessment (RECIST v1.1)****Table 14.4.1: SL-901 Plasma PK Concentrations by Cohort, Visit and Nominal Time****Table 14.4.8: SL-901 Plasma PK Parameters by Cohort and Visit**

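### Laboratory shift tables place each patient in one 'worst' category out of Low, Normal and High, which have no order, so a patient abnormal in both directions has one abnormality dropped

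*SAP*

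**What the plan says.** SAP 11.5.7 sorts laboratory values into three categories. The outer two are "Low: < lower limit of the reference range" and "High: > upper limit of the reference range", with Normal between them, limits included. It then plans the summary: "Shift tables of laboratory parameters from baseline to the worst post-baseline low/normal/high categorization will be performed". The counting unit is the patient, since "percentages will be calculated based on the number of subjects that have valid data for both baseline and at least 1 post-baseline assessment".

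The index in SAP 13.2.1 matches this. Table 14.3.5.7 is "Blood Chemistry – Shift to Worst Post-Baseline Category", and Tables 14.3.5.6 and 14.3.5.8 carry the same single-category title for hematology and coagulation. The other indexed laboratory tables (14.3.5.3 to 14.3.5.5) are by visit, which SAP 11.5.7 describes as absolute values and change from baseline. Outside the tables, "All laboratory parameters, including low/normal/high categorization, will be listed".

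Protocol 9.3.4.1 has the same gap: "Shift tables will be generated to display changes from baseline to the worst value on study and last value on study". It gives no direction for the worst value either. It also plans CTCAE grading and summarized incidences of laboratory abnormalities, but neither SAP 11.5.7 nor the index contains a graded laboratory table.

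**The concern.** A shift to the worst category needs an ordered scale. ECOG status (Table 14.3.5.10) has one, and so does maximum CTCAE grade in the adverse event tables. Low/Normal/High does not: Normal is the best category, but Low and High lie on opposite sides of it. SAP 11.5.7 gives no ranking, no direction of concern by parameter, no combined category, and no separate low and high shifts. The programmer must supply a rule, and two programmers could produce different tables from the same data. Any rule that keeps one category discards a real abnormality for a patient who has both.

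Abnormalities in clinical laboratory evaluations are among the primary safety endpoints (SAP 5.4.1). The shift tables are the only planned summary that classes each patient once across visits from the laboratory values themselves. At stake is whether they show the incidence of low and of high values correctly in small cohorts.

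**Working it through.** The documents give no figure to reproduce, so the check is a reading and a count, followed by an illustration of frequency.

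**1. Is it one category per patient?** This is an inference, but a direct one. The wording is singular, the denominator is patients, and the table titles refer to one category.

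**2. Which parameters can be affected?** Protocol Table 7 includes glucose, potassium, sodium, calcium, magnesium, phosphate, white cells with differential, and platelets. Each can fall below or rise above its range. For some of these the documents suggest a direction of concern: the dose-limiting toxicity list in Protocol 6.4.2 names neutropenia and thrombocytopenia, and Protocol Table 6 names hyperglycemia. For potassium, sodium, calcium, magnesium and phosphate they suggest none.

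**3. Counting one patient.**

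| Baseline | Post-baseline values | Planned table | Separate low and high shifts |
|---|---|---|---|
| Normal | Low once, High once | 1 abnormal shift, direction unspecified | 2: Normal to Low and Normal to High |
| High | Low once, High once | either High to High (unchanged) or High to Low (new) | both shown |

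**4. Weight of one patient.** Cohorts have 3 to 6 patients (SAP section 8). With all of them evaluable, dropping one abnormality lowers the displayed rate in that direction by 1/6 = 16.7 to 1/3 = 33.3 percentage points. In an overall column of 60, the planned maximum for Part 1a, it is 1/60 = 1.7 points. This is the weight of any single patient and says nothing about frequency.

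**5. Frequency, as an illustration only.** Let h and l be the per-visit probabilities of High and Low, and k the number of post-baseline visits. With independent visits,

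P(both) = 1 − (1−h)^k − (1−l)^k + (1−h−l)^k.

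Worked case, h = 0.20, l = 0.05, k = 6: 1 − 0.262 − 0.735 + 0.178 = 0.18.

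| h | l | k = 6 | k = 10 |
|---|---|---|---|
| 0.20 | 0.05 | 0.18 | 0.35 |
| 0.10 | 0.05 | 0.11 | 0.25 |
| 0.10 | 0.02 | 0.05 | 0.11 |

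All three inputs are assumptions, because the text supplied gives no per-visit rates and the schedule of assessments is not readable in it. Independence is also an assumption, and it matters. Keep h = 0.20 and l = 0.05 but let status persist, so that 20% of patients are always High and a different 5% always Low: P(both) is then 0. The range the assumptions allow is therefore 0 to 35%. SAP 11.5.7 also keeps unscheduled results out of the summary tables, which limits the number of values that can enter the shift.

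**The case against.** The strongest reply is that nothing is lost from the trial's safety record. Listings 16.2.8.5 to 16.2.8.7 hold each value with its category, and in cohorts of 3 to 6 a reader can check each patient. Protocol 8.3 requires clinically significant laboratory worsening after the first dose to be considered an adverse event, and the SAP 11.5.2 tables can count one patient under several preferred terms. The maximum tolerated dose rests on counts of dose-limiting toxicities, not on these end-of-study tables. All of this stands, and it limits the consequence to what the shift tables display. A reader might infer that low or high abnormalities vanish from the analysis altogether; the documents do not support that.

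It can also be said that the documents already imply a direction for neutrophils, platelets and glucose, so one sentence defining 'worst' would do. That would settle which abnormality is kept, but the other would still be dropped. For the electrolytes the documents offer no direction to adopt. The general line in SAP 11.2 on categorical variables by time point would not help either, since counts by visit do not give per-patient incidence across visits.

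A second tempting inference is that this trial makes the pattern likely: hyperglycemia is an anticipated toxicity, "In case of hyperglycemia grade 3 or higher, treatment with Metformin is permitted", and Protocol 8.5.2 also permits corticosteroids and hematopoietic growth factors. The documents permit these treatments but do not say that they drive values past the opposite limit. Diabetes requiring medication is excluded in Part 1a, and Part 1b was not started. That inference is not supported, and the 5 to 35% in the working should not be read as an estimate for this study.

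**Conclusion.** The point holds as a defect in how a primary safety endpoint is tabulated. With one category per patient and no order between Low and High, Tables 14.3.5.6 to 14.3.5.8 must drop one abnormality for each patient abnormal in both directions on the same parameter, and the SAP leaves the choice unstated. This follows from the structure of the table and does not depend on any assumed rate. It rests only on reading the tables as one category per patient, as the wording and titles indicate.

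The effect on a cohort rate is 17 to 33 percentage points per affected patient. The number of affected patients cannot be derived from the documents and may be zero. Listings, adverse event tables and dose decisions are unaffected, so this is a worthwhile correction to the SAP and not a threat to the trial's conclusions.

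**What to change.** In SAP 11.5.7, replace the single shift with two per parameter: baseline category to the lowest post-baseline value, judged against the lower limit, and baseline category to the highest post-baseline value, judged against the upper limit. Alternatively, keep one table and add a 'Low and High' post-baseline column. Either way, both abnormalities of such a patient appear. Retitle Tables 14.3.5.6 to 14.3.5.8 to match.

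The cost is a few sentences of SAP text, some programming and slightly longer tables. The values and their categories are already held for the listings, so no new data are needed. SAP section 3 has the plan finalized and signed before database lock, and the rule should be fixed by then. If lock has passed, the change can be recorded in the clinical study report, as Protocol 9.4 provides.
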